9.3.1.3 Supportive Analysis

There will be no supportive analysis for the primary efficacy endpoint.

9.3.1.4 Sensitivity Analysis

MMRM based on Multiple Imputation (MI)

An underlying assumption of the MMRM method is that data are missing at random. To minimize the amount of missing data, subjects who prematurely discontinue study drug treatment will continue to complete all scheduled study visits for spirometry and other efficacy assessments.

To assess the impact of missing data and the assumption that data are missing at random, a multiple imputation algorithm will be used if at least 10% of the subjects have missing changes in ppFEV₁ at Week 4 in any treatment group. Missing absolute change from baseline in ppFEV₁ assessments will be imputed starting from the first visit with missing values, for which all subsequent visits through Week 4 are also missing. For intermediate missing data, i.e., missing values that fall between two non-missing ones, it is reasonable to assume that they are missing at random and therefore will not be imputed. An MMRM analogous to that for the primary analysis of the primary endpoint will be applied to each imputed dataset and the relevant MI estimators will be reported. Details for the MI steps are presented in [Appendix D](#).

9.3.1.5 Subgroup Analysis

Subgroup analyses of the primary efficacy endpoint will be performed using a model similar to that of the primary analysis for each of the following subgroups. The primary result obtained from the model will be the treatment effect at Week 4:

- Age at Screening (<18, ≥18 years)
- ppFEV₁ at baseline (< 70, ≥ 70)
- Sex (male, female)
- Geographic region (North America, Europe)
- Prior use of inhaled antibiotic before the first of study drug in the Treatment Period (Yes, No)

- Prior use of dornase alfa before the first of study drug in the Treatment Period (Yes, No)
- Prior use of inhaled bronchodilator before the first of study drug in the Treatment Period (Yes, No)
- Prior use of inhaled hypertonic saline before the first of study drug in the Treatment Period (Yes, No)
- Prior use of inhaled corticosteroids before the first of study drug in the Treatment Period (Yes, No)
- Prior use of azithromycin before the first of study drug in the Treatment Period (Yes, No)
- Infection with *Pseudomonas aeruginosa* within 2 years prior to screening (Positive, Negative)

The MMRM used for the primary analysis will be used for the subgroup analysis, where the same model will be applied to each category of the subgroup. Note that for the subgroup analysis based on age, the covariate of age at screening (<18 versus ≥ 18 years) from the MMRM will be removed. The adjusted means with 2-sided 95% confidence intervals will be provided. Furthermore, the estimated treatment difference at Week 4 in different categories within a subgroup will also be presented in a forest plot. Note: The results from the subgroup analysis should be interpreted with caution in the cases where sample sizes are small.

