#### **12.3.3.1 Analysis of Primary Variable**

The primary efficacy variable is the absolute change in ppFEV1 from baseline at Week 4. The analysis of this variable will be performed using a mixed-effects model for repeated measures (MMRM) with absolute change from baseline in ppFEV1 at Day 15 and Week 4 as the dependent variable. The model will include treatment group, visit, and treatment-by-visit interaction as fixed effects, with continuous baseline ppFEV1 and age at screening (<18 versus ≥18 years of age) as covariates. The model will be estimated using restricted maximum likelihood.

Denominator degrees of freedom for the *F* test for fixed effects will be estimated using the Kenward-Roger approximation. An unstructured covariance structure will be used to model the within-subject errors. If the model estimation does not converge, a compound symmetry covariance structure will be used instead. Conditional on the observed data and covariates, missing data will be assumed to be missing at random; consequently, no imputation of missing data will be performed.

The primary result obtained from the model will be the estimated treatment difference at Week 4. The adjusted mean with a 2-sided 95% CI and a 2-sided *P* value will be provided. Furthermore, the treatment difference at each post-baseline visit will also be provided, obtained from the model.

Sensitivity analyses for handling missing data will be described in the SAP.

Supportive analyses and subgroup analyses by selected baseline characteristics will also be described in the SAP.

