9.3.1.2 Primary Analysis

The primary analysis will be performed using a mixed-effects model for repeated measures (MMRM) with the absolute change from baseline at Day 15 and Week 4 as the dependent variable. The model will include treatment group, visit, and treatment-by-visit interaction as fixed effects, with continuous baseline ppFEV₁, and age at screening (<18 versus ≥18 years of age) as covariates. The model will be estimated using restricted maximum likelihood.

Denominator degrees of freedom for the F -test for fixed effects will be estimated using the Kenward-Roger approximation². An unstructured covariance structure will be used to model the within-subject errors. If the model estimation does not converge, a compound symmetry covariance structure will be used instead. Conditional on the observed data and covariates, missing data will be assumed to be missing at random; consequently, no imputation of missing data will be performed.

The primary result obtained from the model will be the estimated treatment difference at Week 4. The adjusted means with 2-sided 95% confidence intervals and 2-sided P values will be provided. Furthermore, the treatment difference at each post-baseline visit obtained from the model will also be provided.

The adjusted mean (with SE) obtained from the MMRM analysis at each post-baseline visit up to Week 4 will be plotted by treatment group.

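### Does the subgroup forest plot in SAP 9.3.1.5 need a between-level difference with a confidence interval?

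*SAP*

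**What the plan says.** Protocol 12.3.3.1 hands the subject to the SAP: "Supportive analyses and subgroup analyses by selected baseline characteristics will also be described in the SAP". SAP 9.3.1.5 then lists 11 factors, each with two levels: age, baseline ppFEV1, sex, region, six kinds of prior medication, and *Pseudomonas aeruginosa* infection.

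The primary MMRM is refitted separately, "where the same model will be applied to each category of the subgroup". For the age factor the age covariate is dropped. The outputs are stated in two places: "The adjusted means with 2-sided 95% confidence intervals will be provided", and "the estimated treatment difference at Week 4 in different categories within a subgroup will also be presented in a forest plot". The section closes with a warning: "The results from the subgroup analysis should be interpreted with caution in the cases where sample sizes are small".

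Nothing else in the visible text supplies a between-level contrast. The reused model has treatment-by-visit as its only interaction (SAP 9.3.1.2: "The model will include treatment group, visit, and treatment-by-visit interaction as fixed effects"), and SAP 9.3.1.3 states: "There will be no supportive analysis for the primary efficacy endpoint". Formal testing is confined to the primary and the two key secondary endpoints (SAP 9.3.2.3).

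**The concern.** A forest plot by level invites the question whether the effect differs between levels. The quantity that answers it is the difference between the two level-specific effects with its own interval, and the SAP does not plan one. Each factor would show two estimates, leaving the reader to judge by overlap, or by noting that one interval excludes zero and the other does not. Both are poor guides to heterogeneity, and with 11 factors some apparent differences will arise by chance. The closing warning speaks of small samples, not of the number of comparisons. At stake is the correct reading of an exploratory figure, for instance a claim that the triple combination works less well in one age group or one baseline lung-function group.

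**Working it through.** **Inputs from the documents.** SD 7 points, 50 per arm, 5% dropout, two-sided 0.05, difference 5.0, power about 93% (SAP 7.2, Protocol 12.1); 1:1 allocation (SAP 7.1); 11 two-level factors (SAP 9.3.1.5); Phase 2 F/F changes of 11.0 and 0.4 points (Protocol 9.3.2).

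**Assumptions.** The documents give no subgroup prevalences, so the smaller level's share f is varied from 50% to 20%. SDs are taken as equal across levels and allocation as 1:1 within each level. Any gain from the covariates or the Day 15 data is ignored.

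**Step 1: the plan's own figure.** Evaluable per arm: 50 × 0.95 = 47.5. SE of the overall difference: 7 × √(2/47.5) = 1.436. The noncentral t with 93 df and noncentrality 5/1.436 = 3.48 gives power 93.1%, so the stated 93% reproduces. The overall 95% half-width is 1.986 × 1.436 = 2.85 (2.82 with 1.96).

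**Step 2: precision of a between-level gap.** Level i, with nᵢ per arm, has SEᵢ = 7 × √(2/nᵢ). The levels are disjoint subjects fitted separately, so SE(gap) = √(SE₁² + SE₂²). Satterthwaite df are SE(gap)⁴ / (SE₁⁴/df₁ + SE₂⁴/df₂), with dfᵢ = 2nᵢ − 2.

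| Split | SE₁, SE₂ | SE(gap) | Ratio to 1.436 | df | t | 95% half-width |
|---|---|---|---|---|---|---|
| 50/50 | 2.03, 2.03 | 2.87 | 2.00 | 91.0 | 1.986 | 5.7 |
| 30/70 | 2.62, 1.72 | 3.13 | 2.18 | 50.3 | 2.008 | 6.3 |
| 20/80 | 3.21, 1.61 | 3.59 | 2.50 | 26.2 | 2.055 | 7.4 |

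The ratio equals 1/√(f(1 − f)) and does not depend on the SD.

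**Step 3: how often the display could mislead.** With the same true effect in both levels, P(|gap| ≥ 5) = 2{1 − Φ(5/SE(gap))}. At SD 7 this is 0.082, 0.111 and 0.164 for the three splits. For 11 independent factors at 50/50, 1 − (1 − 0.082)¹¹ = 0.61. Assuming SD 6 or 5 instead, it is 0.38 or 0.15. Simulation with an assumed latent correlation of 0.5 between factors gave 0.52, 0.33 and 0.14 at SD 7, 6 and 5. The 5-point threshold is borrowed from the overall design effect; the documents set no margin for heterogeneity.

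The chance that exactly one level's interval excludes zero is p₁(1 − p₂) + p₂(1 − p₁), with pᵢ the within-level power. At SD 7 and a true effect of 5.0 it is 44% (50/50) to 64% (20/80). At 11.0 − 0.4 = 10.6, the Phase 2 gap, it is 0.2% to 13%.

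**Step 4: what the added contrast would deliver.** At SD 7, its power for a true 5-point gap, using the Satterthwaite interval, is 41%, 35% and 27% for the three splits. With no heterogeneity and independent factors, the chance that at least one of 11 such intervals excludes zero is 1 − 0.95¹¹ = 0.43.

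**Step 5: what would change in the results.** The level estimates, primary estimate, testing order and type I error all stay the same. The new line is d₁ − d₂ with √(SE₁² + SE₂²), both taken from fits already planned.

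**The case for a change.** The best case for a change is that the omission is real and cheap to cure. Protocol 9.3.1 itself says that response may depend on ppFEV1, and baseline ppFEV1 is one of the 11 factors, so readers will look for a difference there. Even the most favourable split doubles the interval width. Chance gaps arise whatever the size of the true effect, so a strong overall result does not remove them. One sentence and one derived line per factor would put the uncertainty on the page.

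Much of this stands. The text has been read correctly, the arithmetic holds under its assumptions, and the closing caution does not mention 11 unadjusted comparisons. Two points weaken it. First, the caution already reaches most of the display: 47.5 per arm leaves about 24 per arm in each level at 50/50 and 9.5 per arm in the smaller level at 20/80. Second, the contrast replaces one misreading with others. Eleven intervals for differences can be read as eleven 5% tests even without P values, and wide intervals that cover zero can be mistaken for evidence of consistency.

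One caveat runs the other way. SAP 9.3.1.5 attaches intervals expressly to the adjusted means. That the plotted treatment differences also carry intervals is the ordinary meaning of a forest plot rather than a stated rule; an analyst would supply them as a matter of course.

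**Conclusion.** No change to the plan is needed. SAP 9.3.1.5 describes an exploratory display and makes no claim about heterogeneity. Neither the primary nor the secondary objectives (Protocol 6, SAP 5) ask about effect modification, and subgroups sit outside the testing hierarchy. The omission biases no estimate and alters no planned conclusion.

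It does leave readers without a direct view of how imprecise a between-level gap is: about ±5.7 to ±7.4 points against ±2.85 overall, at SD 7 with equal SDs and 1:1 allocation within levels, for assumed splits from 50/50 to 20/80. Baseline adjustment in the MMRM could narrow these figures.

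The contrast can be derived from the reported level estimates and their standard errors, so it can be added to the study report without touching a model. Whoever adds it should label it exploratory, give no P value, and say that about 43% of trials would show at least one of 11 intervals excluding zero by chance under independence and a uniform effect. That is a reporting choice on which statisticians may reasonably differ.

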9.3.2 Analysis of Key Secondary Variables

9.3.2.1 Definition of Variables

Sweat chloride (SwCl): the SwCl value for a given visit will be calculated as the mean of the non-missing sweat chloride measurements obtained on the left and right arms at that visit. If one of the two arm measurements at a time point is missing, the other will be used as the mean. A volume ≥ 15 μL is required for an accurate determination of sweat chloride. Any results reported as having volume < 15 μL will be considered missing. Any sweat chloride values reported as < 10 mmol/L or > 160 mmol/L will be considered missing.

Cystic Fibrosis Questionnaire-Revised (CFQ-R): The CFQ-R^{3,4,5} is a validated CF-specific instrument that measures quality-of-life domains. This study utilizes three different versions of CFQ-R:

- CFQ-R for Children ages 12 and 13
- CFQ-R for Adolescents and Adults (subjects 14 years and older)
- CFQ-R for Parents/Caregivers (subjects 13 years and younger)

In all three versions, specific question belonging to a domain is scored 1, 2, 3, or 4. The CFQ-R domain score, e.g., physical domain score or respiratory domain score, is defined as a scaled score as follows:

Scaled score for a domain = $100 \times (\text{mean (scores of all questions in the domain)} - 1)/3$, where the score from a negatively phrased question is first reversed, i.e., reversed score = $5 - \text{actual score}$, so that 1 always represents the worst condition and 4 the best condition. The (scaled) domain score ranges from 0 (worst condition) to 100 (best condition). The scaled score

for a specific domain will not be calculated if more than half of the questions in the domain have missing scores.

The (scaled) domain score from the CFQ-R for Children ages 12 and 13 and for Adolescent and Adults will be pooled for the analysis purpose.

9.3.2.2 Analysis Method

Absolute change in SwCl from baseline at Week 4:

Analysis of absolute change from baseline in sweat chloride will be based on an MMRM similar to the primary analysis of the primary efficacy variable. The model will include treatment, visit, and treatment-by-visit interaction as fixed effects with continuous baseline ppFEV₁, and age at screening (<18 versus ≥18 years of age) as covariates.

Absolute change in CFQ-R respiratory domain score from baseline at Week 4:

[figure not shown]
Analysis of absolute change from baseline in CFQ-R respiratory domain score will be based on an MMRM similar to the primary analysis of the primary efficacy variable. The model will include treatment, visit, and treatment-by-visit interaction as fixed effects with continuous baseline ppFEV₁, and age at screening (<18 versus ≥18 years of age) as covariates.

The LS mean (SE) of the within-treatment group change from baseline at each post-baseline visit up to Week 4 along with the 95% CI will be estimated from the corresponding MMRM. The LS mean (SE) of the treatment difference between VX-445/TEZ/IVA and TEZ/IVA at each post-baseline visit will be provided along with the corresponding 95% CI and *P* value. The LS mean (SE) at each visit will also be plotted by treatment group. In addition, the post-baseline raw values and the absolute change from baseline at each post-baseline visit up to Week 4 will be summarized descriptively (n, mean, SD, median, minimum, and maximum).

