### 9.1.2 Tezacaftor/Ivacaftor Run-in Period

The TEZ/IVA Run-in Period has a 4-week duration and is designed to establish a reliable on-treatment (TEZ/IVA) baseline for the Treatment Period. The first dose of open-label TEZ/IVA will be administered at the Day -28 Visit. The last dose of open-label TEZ/IVA will be administered in the evening on Day -1 (1 day before the Day 1 Visit).

On Day -14, spirometry and SwCl will be assessed. The Day -14 spirometry assessment will be used for stratification of randomization ([Section 9.2](#)).

Subjects who prematurely discontinue study drug treatment during the Run-in Period will not be randomized or participate in the Treatment Period ([Section 9.1.5.1](#)).

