9 STATISTICAL ANALYSIS

9.1 General Considerations

The Schedule of Assessments is provided in Section 3 of CSP. The precision standards for reporting safety and efficacy variables are provided in an internal Biometrics document that specifies the programming rules including the precision for derived variables.

Continuous variables will be summarized using the following descriptive summary statistics: the number of subjects (n), mean, SD, median, minimum value (min), and maximum value (max).

Categorical variables will be summarized using counts and percentages. Percentages will be presented to 1 decimal place.

Baseline value, unless otherwise specified, is defined as the most recent non-missing measurement (scheduled or unscheduled) collected before the first dose of study drug in the Treatment Period.

Absolute change from baseline will be calculated as post-baseline value – baseline value.

Relative change from baseline will be calculated as (post-baseline value – baseline value)/baseline value.

The **Treatment-emergent (TE) Period for the Run-in Period** will be from the first dose of study drug in the Run-in Period to

- 1) for subjects who complete the run-in period and continue to the Treatment Period, the first dose of study drug in the Treatment Period, or

- 2) for subjects who do not continue to the Treatment Period, either 28 days after the last dose date of study drug in the Run-in Period, or to the completion of study participation date, whichever occurs first.

The **TE Period for the Treatment Period** will include the time from the first dose date of study drug in the Treatment Period (TC or placebo + TEZ/IVA) to 28 days after the last dose of the study drug or to the completion of study participation date, whichever occurs first.

Unscheduled visits: Unscheduled visit measurements will be included in analysis as follows:

- 1) In scheduled visit windows per specified visit windowing rules
- 2) In the derivation of baseline and last on-treatment measurements
- 3) In the derivation of maximum and minimum values during TE period, and maximum and minimum change from baseline values during TE period for safety analyses
- 4) In individual subject data listings as appropriate

Visit windowing rules: The analysis visit windows for protocol-defined visits are provided in [Appendix A](#).

Incomplete/missing data will not be imputed, unless specified otherwise.

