9.2.2 Demographics and Baseline Characteristics

Demographics and baseline characteristics will be summarized based on the FAS, and presented by treatment group and overall, as applicable.

Demographic data will include the following:

- Age at baseline (in years)
- Sex (female and male)
- Ethnicity (Hispanic or Latino, not Hispanic or Latino, and not collected per local regulations)
- Race (White, Black or African American, Asian, American Indian or Alaska Native, Native Hawaiian or Other Pacific Islander, and not collected per local regulations)
- Geographic region (North America, Europe)

Baseline characteristics will include the following:

- Weight (kg)
- Height (cm)
- BMI (kg/m²)

Stratification categories will include the following:

- Age at Screening Visit (<18, ≥18 years)
- ppFEV₁ at Day -14 (<70, ≥70)

Disease characteristics will include the following:

- ppFEV₁ at baseline (<40, ≥ 40 to <70, ≥70 to ≤90, and >90)
- ppFEV₁ at baseline (continuous)
- Sweat chloride at baseline (continuous)
- CFQ-R respiratory domain score at baseline (continuous)
- Prior use of dornase alfa before first dose of study drug in the Treatment Period (Yes, No)

- Prior use of azithromycin before first dose of study drug in the Treatment Period (Yes, No)
- Prior use of inhaled antibiotic before first dose of study drug in the Treatment Period (Yes, No)
- Prior use of bronchodilator before first dose of study drug in the Treatment Period (Yes, No)
- Prior use of inhaled bronchodilator before first dose of study drug in the Treatment Period (Yes, No)
- Prior use of inhaled hypertonic saline before first dose of study drug in the Treatment Period (Yes, No)
- Prior use of inhaled corticosteroids before first dose of study drug in the Treatment Period (Yes, No)
- Infection with *Pseudomonas aeruginosa* within 2 years prior to screening (Positive, Negative)

In addition, data listings will also be provided for:

- Informed consent;
- Inclusion/Exclusion criteria violation for subjects with any such violations.

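### The sweat chloride and CFQ-R change-score models omit each endpoint's own baseline; adding it, with a visit interaction, could improve precision at almost no cost

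*SAP*

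**What the plan says.** SAP 9.3.2.2 writes out the terms of both key secondary models. The sweat chloride model has treatment, visit and the treatment-by-visit "interaction as fixed effects with continuous baseline ppFEV₁, and age at screening (<18 versus ≥18 years of age) as covariates". The CFQ-R sentence begins "Analysis of absolute change from baseline in CFQ-R respiratory domain score will be based on an MMRM similar to the primary analysis" and ends with the same covariate list. No other covariate and no covariate-by-visit term appears.

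The list matches the primary model in SAP 9.3.1.2, where treatment-by-visit is followed by "interaction as fixed effects, with continuous baseline ppFEV₁, and age at screening (<18 versus ≥18 years of age) as covariates". The response is a difference (SAP 9.1): "Absolute change from baseline will be calculated as post-baseline value – baseline value".

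Both own baselines are available. Protocol Table 3-2 schedules sweat chloride and CFQ-R on Day 1, and SAP 9.2.2 summarizes both as continuous baseline characteristics. Neither is a stratification factor: SAP 7.3 stratifies on Day -14 ppFEV1 (split at 70) and age group. Protocol 12.3.3.2 says only that these models resemble the primary one, includes Day 15 and Week 4, and leaves details to the SAP.

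**The concern.** In the primary model, baseline ppFEV1 does two jobs: it relates to a stratification factor, and it is the endpoint's own baseline. In the sweat chloride and CFQ-R models only the first job remains.

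A change score subtracts the whole baseline, which fixes the slope of the Week 4 value on baseline at 1. If the true slope is different, part of any chance imbalance between the groups in baseline sweat chloride or CFQ-R stays in the estimated treatment difference. Over repeated randomizations this averages to zero, so there is no bias, but it adds variance. At stake are confidence intervals wider than they need to be for the two formally tested key secondary endpoints. CFQ-R is tested only if sweat chloride succeeds, so precision on sweat chloride also affects access to the CFQ-R test.

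**Working it through.** **The plan's own figure.** The only power statement concerns ppFEV1: difference 5.0, SD 7, 50 per group, 5% dropout, 2-sided 0.05 (Protocol 12.1, SAP 7.2). With 50 × 0.95 = 47.5 per group, the noncentrality is 5 / (7 × √(2/47.5)) = 3.48, and the exact t-test power is 93.1%. The stated 93% reproduces and is unaffected by this point. There is no corresponding SD, effect size or power for sweat chloride or CFQ-R, so the inputs below are assumptions.

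**Equal slopes at both visits and in both groups.** Let s be the baseline SD, ks the Week 4 SD, and r the correlation of baseline with the Week 4 value. The Week 4 slope on baseline is rk. Baseline ppFEV1 and age group are taken as unrelated to the change.

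- Variance of the change score: s²(1 + k² − 2rk)
- Variance after own-baseline adjustment: s²k²(1 − r²)
- Difference: s²(1 − rk)², which is zero when rk = 1
- Ratio, adjusted over planned: k²(1 − r²) / (1 + k² − 2rk), which is (1 + r)/2 at k = 1

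For example, at r = 0.7 and k = 0.8: 0.64 × 0.51 / (1.64 − 1.12) = 0.3264/0.52 = 0.628. At r = 0.7 and k = 1.2: 0.7344/0.76 = 0.966.

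| k | r = 0.5 | r = 0.7 | r = 0.8 | r = 0.9 |
|---|---|---|---|---|
| 0.8 | 0.57 | 0.63 | 0.64 | 0.61 |
| 1.0 | 0.75 | 0.85 | 0.90 | 0.95 |
| 1.2 | 0.87 | 0.97 | 1.00 | 0.98 |

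The interval narrows by 1 − √ratio; at k = 1 that is 13%, 8%, 5% and 3%. A ratio of 0.75 is worth raising 47.5 evaluable subjects per group to 47.5/0.75 = 63, and a ratio of 0.95 to 50.

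If baseline ppFEV1 correlates 0.2 to 0.4 with the endpoint at both times (k = 1), the ratio moves little: 0.74 to 0.70 at r = 0.5, and 0.84 to 0.82 at r = 0.7.

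**Simulation check.** Day 15 and Week 4 change scores were simulated for 95 complete subjects (100 less 5%) with no treatment effect. The fit used an unstructured covariance by iterated generalized least squares, without the Kenward-Roger adjustment, with 3,000 to 8,000 runs in each of 25 scenarios. With own baseline and its visit interaction added, the ratios at k = 1 were 0.756, 0.858, 0.909 and 0.960, close to the formula. Type I error was 4.2% to 5.6% for the planned model and 4.3% to 5.8% with the added terms (Monte Carlo SE 0.2 to 0.4 points).

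**Slopes that differ by visit.** Simulated variance ratios against the planned model:

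| Slope, Day 15 / Week 4 | Own baseline, one common slope | Own baseline with visit interaction |
|---|---|---|
| 0.8 / 1.0 | 1.09 | 1.01 |
| 0.7 / 1.0 | 1.11 | 1.01 |
| 0.7 / 0.9 | 1.03 | 0.99 |
| 0.8 / 0.7 | 0.89 | 0.88 |
| 0.5 / 1.0 (extreme) | 1.28 | 1.01 |
| 1.0 / 1.0 | 1.01 | 1.01 |

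A single slope forced on both visits can lose precision at Week 4. The interaction removes nearly all of that loss and keeps the gain.

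**Slopes that differ by treatment group.** With mean slope m, difference d, residual variance v and s = 1, the ratio is (v + d²/4) / (v + d²/4 + (1 − m)²). With v = 0.5 and d = 0.4 this gives 0.54/0.63 = 0.857 at m = 0.7, 0.54/0.58 = 0.931 at m = 0.8, and 1.000 at m = 1.0. The simulated values with the interaction were 0.87, 0.94 and 1.01.

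**The case against.** The planned models are valid, and nothing in the documents shows that either endpoint is short of precision, so no changed conclusion can be demonstrated. That stands, and it makes this an optional improvement.

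The gain may be small, above all for sweat chloride. The run-in is "designed to establish a reliable on-treatment (TEZ/IVA) baseline for the Treatment Period" (Protocol 9.1.2), and each sweat chloride value is "calculated as the mean of the non-missing sweat chloride measurements obtained on the left and right arms at that visit" (SAP 9.3.2.1). Both tend to raise the correlation of baseline with Week 4. At k = 1.2 and r of 0.7 or more the gain is 0% to 3%, about the size of the cost. That stands too.

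The visit interaction may be more than is needed. Every loss shown for a common slope has the slope rising from Day 15 to Week 4, which the documents give no reason to expect. With flat or falling slopes the main effect alone did not lose: in further simulations, slopes of 0.7/0.7 gave 0.87 without and 0.88 with the interaction, 0.7/0.6 gave 0.80 both ways, and 0.9/0.7 gave 0.92 and 0.88. So the main effect alone would often do. But in these cases the interaction was at worst 0.01 behind and up to 0.04 ahead, and it protects against the rising case. It remains the safer choice.

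Finally, the primary model has no visit interaction for its own baseline, and the key secondary models are meant to resemble it. The difference in structure is real. However, Protocol 12.3.3.1 lists the primary covariates, whereas Protocol 12.3.3.2 leaves the details of these two models to the SAP.

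**Conclusion.** The point holds as an optional, low-cost gain in precision. The planned analyses are not in error. How much is gained cannot be settled from the documents. At equal SDs the variance saving is 25% to 5% for correlations of 0.5 to 0.9; it is larger if the SD falls by Week 4 and close to nil if the Week 4 slope is near 1. These figures are illustrations, not bounds. They assume that baseline ppFEV1 and age group are unrelated to the change and, for the main table, a common slope across visits and groups. With the visit interaction, the adjusted model was never materially worse than the planned one in any case examined.

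**What to change.** Before database lock and unblinding, amend SAP 9.3.2.2:

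- Sweat chloride model: add continuous baseline sweat chloride and its interaction with visit.
- CFQ-R model: add continuous baseline CFQ-R respiratory domain score and its interaction with visit.
- Keep baseline ppFEV1 and age group in both. Do not add the main effect alone, because it forces one slope on both visits.

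The cost is two terms in each of two sentences. The protocol need not change, since Protocol 12.3.3.2 defers to the SAP, and SAP 4 provides for an amendment before lock. No new data are needed and no subject is lost, because a change score already requires the baseline. The statistical price is two parameters per model: ratios of 1.008 to 1.013 in the simulated no-gain cases, so allow 1% to 2% of Week 4 variance.
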